7.1 Study Subjects

7.1.1 Disposition of Subjects

Subject disposition will be summarized with frequency tables.

7.1.2 Analysis Sets

All subject data that satisfied the inclusion and exclusion criteria will be included in this analysis.

7.2 General Methodology

All statistical analyses will be performed using Statistical Analysis System (SAS) for Windows (version 9.2 or higher, SAS Institute Inc. Cary, NC) or other widely accepted statistical or graphical software. In general, data for all study subjects will be presented. Individual data will be presented in subject listings.

Descriptive statistics will be used to present the data and to summarize study outcomes. Discrete variables will be presented using frequency distributions and cross tabulations. Continuous variables will be summarized by presenting the number of observations (N), mean, standard deviation, median, minimum, and maximum values.

7.2.1 Statistical Method

Descriptive statistics will be used to summarize study outcomes. Subjects with valid recorded data from the study device (EEG signals) and a completed eCRF will be included in the primary analysis.

The relationships between BIS parameters, age, physical and cognitive state, and depth of anesthesia in patients undergoing surgery under general anesthesia will be assessed. Also, the relationship between BIS and MOAA/S will be examined by subjects under 65 and by subjects over 65 years old. Pearson's correlation or Spearman's rank correlation will be calculated as appropriate. Continuous variables will be evaluated using analysis of variance (ANOVA) or nonlinear E_{max} model, and categorical variables will be evaluated using the chi-square or Fisher's exact test, as well as multivariate logistic regression with age as an explanatory factor. A P-value of less than 0.05 is considered statistically significant unless otherwise specified.

Specifically, for the primary objective, a polytomous logistic regression model will be employed to assess the relationship between the MOAA/S scale and the BIS score/age groups (18-64 vs. 65+). The interaction between age and BIS score will be included. Another dichotomous logistic regression model will be utilized as well, when the MOAA/S scale is classified as responsive (scale of 2, 3, 4, and 5) and non-responsive (scale of 0 and 1).

The BIS scores at various time stamps (e.g., first response, extubation, etc) will be compared between the two age groups.

A simplified Sigmoid E_{max} model will also be used to analyze the relationship between the BIS™ index and loss of responsiveness through the probability of response curves. The values of BIS™ at which 50% (BIS_{50}) and 95% (BIS_{95}) of subjects are unresponsive, and their 95% confidential intervals will be derived. The systematic variance between groups will be evaluated.

The model is as follows:

$$P = \frac{e^{a+bX}}{1 + e^{a+bX}}$$

where P is the probability of "unresponsive", X is the explanatory variable (BIS™ value or anesthetic agent concentration on the log scale), and a & b are model parameters.

For each age subgroup, one can estimate the BIS™ value and the effect-site concentration at which 50% subjects are unresponsive, i.e., BIS_{50} and EC_{50} respectively. The corresponding 95% confidence intervals and standard errors for the estimates will be derived. The same evaluation will be performed for BIS_{95} , at which 95% subjects are unresponsive. The systematic variance between groups will be evaluated accordingly.

Multivariate logistic regression model will be used to study the effects of other baseline covariates (gender, blood panel, physical and cognitive states).

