5.1.4 Secondary Endpoint

Assessments of the subject's demographics, age and blood panel as well as the physical and cognitive state using:

- Mini Mental State Examination (MMSE)
- Mini Nutritional Assessment (MNA®-SF)

- Edmonton Frail Scale (EFS)

6. Study Design

This is a multicenter, non-invasive, interventional data collection study to improve the current BIS™ algorithm. Subjects undergoing a standard of care, elective non-ambulatory surgery under general anesthesia will be recruited. Eligible patients 18 years and older, will be informed of the study and invited to participate. Each eligible and consented subject will undergo the study assessments and procedures. The BIS™ sensors will be applied to the patient's forehead before anesthesia is administered. The BIS™ data will be collected throughout the surgery. The data recorded during the surgery will be provided to Medtronic.

It is planned to enroll up to 100 subjects from 2 centers. It is anticipated that approximately 35% of enrolled patients will be between ages 18-64 years old, and approximately 65% of patients will be above the age of 65 years. In addition to basic demographic data collection, three assessments, the Mini Mental State Examination (MMSE), the Mini Nutritional Assessment (MNA®-SF), and the Edmonton Frail Scale (EFS) will be administered to each subject prior to surgery.

Study sites that enroll faster than others will be allowed to do so in order to maintain an adequate enrollment rate.

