10.6.3 Induction Period

During the induction procedure, subjects will be pre-medicated per institutional guidance. All pre-medications, doses, and times of administration will be recorded in the eCRFs.

Prior to induction, subjects will be assessed using the Modified Observer's Assessment of Alertness/Sedation Scale (MOAA/S) which can be referenced in Appendix A.

A slower induction of anesthesia will be achieved by setting a lower initial target propofol dose and making an incremental increase in the targeted dose. This is a conservative approach which maintains consistency across all study subjects and will ensure safety of the elderly patients included in the study, which should also closely align with standard institutional practices. The propofol will be administered using target-controlled infusion (TCI) pump, and the initial targeted effective site concentration (Ce) will be half of the effective site propofol concentration dosage based on drug Instructions for Use (IFU) based on the subject's body mass used for induction. The TCI will calculate the initial bolus and infusion rate required to rapidly achieve and maintain this drug level based on propofol's population pharmacokinetics using the Schnider Model. At this step, the depth of anesthesia will be assessed using MOAA/S after an equilibrium time of approximately 5 minutes (from the start of propofol infusion.) After this initial step, the target effect site concentration is subsequently adjusted in an attempt to maintain the desired level of sedation and three-quarters of the Ce will be administered. This second step will also require depth of anesthesia assessment using MOAA/S after an equilibrium time of approximately 5 minutes. Lastly, the final/full Ce dose of the propofol will be administered, and the MOAA/S will be assessed after another equilibrium time of 5 minutes is reached. The specified induction period will last approximately 15 minutes in order to record and monitor the BIS values, EEG readings, and MOAA/S scores across the anesthetic agent introduction into the subject.

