4.2 Secondary Objective

The secondary objective is to investigate BIS parameters, depth of anesthesia and physical and cognitive states in the study populations using the following tools:

- Mini Mental State Examination (MMSE)
- Mini Nutritional Assessment (MNA®-SF)
- Edmonton Frail Scale (EFS)

5 Study Design

This is a multicenter, non-invasive, interventional data collection study to improve the current BIS algorithm. Subjects undergoing a standard of care, elective non-ambulatory surgery under general anesthesia will be recruited. Eligible patients 18 years and older, will be informed of the study and invited to participate. Each eligible and consented subject will undergo the study assessments and procedures. The BIS™ sensors will be applied to the patient's forehead before anesthesia is administered. The BIS data will be collected throughout the surgery. The data recorded during the surgery will be provided to Medtronic.

It is planned to enroll up to 200 subjects from approximately 5 centers. It is anticipated that approximately 35% of enrolled patients will be between ages 18-64 years old, and approximately 65% of patients will be above the age of 65 years. In addition to basic demographic data collection, three assessments, the Mini Mental State Examination (MMSE), the Mini Nutritional Assessment (MNA®-SF), and the Edmonton Frail Scale (EFS) will be administered to each subject prior to surgery.

Study sites that enroll faster than others will be allowed to do so in order to maintain an adequate enrollment rate. To retain a good balance however, no more than 50% of total subjects expected to enroll at an individual study site.

6 Determination of Sample Size

Up to 200 subjects will be enrolled in the study, with 65% subjects over the age of 65 years. The sample size will provide adequate data information to assess the age impact for elder subjects with greater than 90% power to detect a distributional shift of BIS and MOAA/S scores between ages 18-64 and ≥ 65 years old (BIS 5-point, MOAA/S 0.5-point). Sample size calculations are based on the PASS software with a standard deviation of 10-point for BIS and 1.2 for MOAA/S. The sample size will also ensure high confidence to detect any rare safety events with an incidence as low as 2% (>98% confidence) or 1% (>86% confidence).

7 Statistical Methods

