7.3 Center Pooling

There are five participating centers in this study. Clinical procedure and data collection were executed under the same protocol. Every effort will be made to promote consistency in study execution at each study site.

Data poolability across sites will be assessed descriptively. Summary statistics of the primary outcomes (BIS, MOAA/S) will be presented by site, and statistical inferences may be provided for reference purposes. If the sites are found to be significantly heterogeneous, additional analyses will be conducted to further assess the differences between sites in baseline and procedural variables that might contribute to the differences.

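### The age-group BIS50 contrast has no site term, so a center difference that coincided with age mix would be read as an age effect

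*SAP*

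**What the plan says.** The analysis of BIS against responsiveness is in SAP 7.2.1.

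- **Per-group curves.** The probability of being unresponsive is exp(a+bX)/(1+exp(a+bX)), with a and b as the only parameters. The curves are fitted by age group: "For each age subgroup, one can estimate the BIS™ value and the effect-site concentration at which 50% subjects are unresponsive". The same is planned for BIS95.
- **Primary-objective models.** A polytomous logistic model relates MOAA/S to BIS and age group (18-64 vs 65+). The text continues: "The interaction between age and BIS score will be included. Another dichotomous logistic regression model will be utilized as well". The dichotomous model sets MOAA/S 0-1 against 2-5.
- **Covariates.** "Multivariate logistic regression model will be used to study the effects of other baseline covariates (gender, blood panel, physical and cognitive states"). Site is not in the list.
- **Site.** SAP 7.3 summarises BIS and MOAA/S by site, with inference for reference only. It adds: "If the sites are found to be significantly heterogeneous, additional analyses will be conducted to further assess the differences between sites", looking at baseline and procedural variables. No site-adjusted age contrast is named.
- **Centers.** The SAP follows protocol version 4 (200 subjects, five centers). Its section 5 expects "no more than 50% of total subjects expected to enroll at an individual study site". Protocol 5.1, section 6, says: "It is planned to enroll up to 100 subjects from 2 centers". It lets faster sites enroll more and states no cap. The split of about 35% aged 18-64 and 65% older is anticipated overall, not set per center.

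**The concern.** The study aims to improve the index in the elderly, and an age-group difference in BIS50 is a planned result that could prompt an age adjustment. If one center tended to record higher BIS at loss of response and also enrolled more older patients, the pooled per-group curves would attribute part of that center difference to age. With two centers there is little chance for such differences to average out.

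A center difference is possible. Protocol 10.6.3 says "subjects will be pre-medicated per institutional guidance. All pre-medications, doses, and times of administration will be recorded in the eCRFs", and protocol 7.5.5 notes that some combinations of sedatives and analgesics can leave unconscious patients with BIS above 60. Protocol 14.1 describes an unpowered feasibility study, so the estimate itself matters more than its p-value.

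**Working it through.** The plan gives no figure for a site effect or for age mix by site, so these inputs are assumed. For scale, SAP section 6 plans for a 5-point BIS shift with SD 10. At 70 vs 130 subjects, z = 5/(10 x sqrt(1/70+1/130)) = 3.37 and power = Phi(3.37-1.96) = 92.1%, which agrees with the SAP's claim of more than 90%. That claim belongs to 200 subjects; protocol 5.1 claims no power.

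**Step 1: expected shift.** Let w be the share of subjects at center A, pA and pB the proportions aged 65+ at each center, p the overall proportion, and D the center difference in BIS50. The proportion from center A is w pA/p in the older group and w(1-pA)/(1-p) in the younger. The gap is

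share difference = w(1-w)(pA-pB)/[p(1-p)], and shift in the contrast = share difference x D.

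Example, 80% vs 50% at equal enrolment: 0.40/0.65 - 0.10/0.35 = 0.615 - 0.286 = 0.33.

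| Aged 65+, A / B | w | p | Share difference | Shift, D=3 | Shift, D=5 |
|---|---|---|---|---|---|
| 65% / 65% | 0.5 | 0.65 | 0.00 | 0.0 | 0.0 |
| 70% / 60% | 0.5 | 0.65 | 0.11 | 0.3 | 0.6 |
| 80% / 50% | 0.5 | 0.65 | 0.33 | 1.0 | 1.7 |
| 80% / 50% | 0.8 | 0.74 | 0.25 | 0.8 | 1.3 |
| 80% / 50% | 0.2 | 0.56 | 0.19 | 0.6 | 1.0 |

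The 50% cap would not help: of the three 80/50 rows, equal enrolment gives the largest shift.

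**Step 2: simulation with no true age effect.** There were 100 subjects, two centers and 2,000 replicates per scenario. Each subject had four BIS-MOAA/S pairs, matching the four assessments in protocol 10.6.3 (mean BIS 95/75/60/45, SD 10). A subject was unresponsive below a personal threshold (mean 65, SD 6 or 10, plus the center shift). The model had BIS, age group and interaction, which is equivalent to separate curves per group, with small-sample-corrected cluster-robust standard errors. The SAP names no method for repeated assessments, so these error rates are illustrative.

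80% / 50% at equal enrolment, without a site term:

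| Threshold SD | D | Shift | SD of contrast | Shift / SD | False positives |
|---|---|---|---|---|---|
| 6 | 3 | 1.02 | 1.81 | 0.56 | 7.7% |
| 6 | 5 | 1.66 | 1.92 | 0.86 | 13.9% |
| 10 | 3 | 0.95 | 2.58 | 0.37 | 6.4% |
| 10 | 5 | 1.62 | 2.58 | 0.63 | 7.5% |

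- A repeat of the second row gave about 1.6 points and 15%, falling to about 0.1 or less and 6% with a site term.
- At 70% / 60%, false positives were 4-5%. With uneven enrolment at 80% / 50% they were 5-9%.
- A fifth pair per subject left the 80/50 result at 0.96-1.71 points and 7-14%.
- Across these scenarios, a site term brought the contrast to within 0.15 points of zero, with false positives of 4-6%.

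A differently built simulation (common slope, no interaction, ordinary standard errors, D=5) gave 1.04 points and 9.4% at a share difference of 0.2. At 0.4, beyond the 80/50 case, it gave 1.99 points and 16.6%.

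**Step 3: what a site term does not correct.** Let the centers differ in spread only (threshold SD 6 vs 10), with an 80/50 mix and no mean shift. The age-by-BIS interaction test was then falsely positive in 11% of trials without a site term and 11-12% with it. The BIS95 contrast was off by 1.8 and 1.9 points respectively. A repeat gave near 10% and about 2 points.

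**Step 4: cost.** At 80/50 with equal enrolment the center-by-age counts are 40, 10, 25 and 25. The correlation is (40x25 - 10x25)/sqrt(50x50x65x35) = 0.314, so the standard error grows by sqrt(1/(1-0.099)) = 1.05. In simulation it ranged from 4% smaller to 7% larger.

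**The case against.** The strongest reply concerns materiality. The documents give neither a center difference nor an age mix by center. At equal mix the shift is zero, and at 70/60 it is negligible. The 14-15% rate needs an 80/50 mix, a 5-point difference, equal enrolment and a threshold SD of 6 together. The plan also limits center differences: protocol 10.6.3 says of the stepwise propofol induction, "This is a conservative approach which maintains consistency across all study subjects". SAP 7.3 would examine baseline variables if sites differed, and age is one, so an uneven mix could surface there. The SAP also permits further exploratory analyses. All of this stands and keeps the point minor. It does not supply an adjusted contrast.

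Four stronger readings are tempting but unsupported.

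- A reader might infer that the age result is biased. Nothing in the documents shows that site tracks age.
- A reader might infer that one site term removes any site artefact, or that the interaction test is safe. Step 3 shows otherwise when spread differs.
- A reader might infer that SAP 7.3 would usually miss the problem. In the 80/50 case a test of the site coefficient given BIS reached p<0.05 in 18-72% of simulated trials. But SAP 7.3 works from site summaries and does not define significant heterogeneity, so that figure does not measure it. It only argues for not making the adjustment conditional on significance.
- A reader might infer that two age groups are an error because they cannot show change within the elderly. SAP 7.2.1 also plans correlations and a logistic regression with age, without fixing the coding, so age in years is not excluded.

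**Conclusion.** The point holds in a limited form and is of low severity. No listed model contains site, and SAP 7.3 produces no site-adjusted age contrast. The current protocol has two centers and does not control age mix by center. The BIS50 age contrast is therefore open to a center difference in mean threshold, but only if age mix also differs between centers.

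With an assumed 3-5 point center difference, the size runs from zero through a negligible 0.3-0.6 points to 1.0-1.7 points. The last range is 0.4-0.9 of the contrast's own standard deviation and goes with false-positive rates of 6-15%. These figures concern BIS50 only. They do not cover BIS95, the interaction test or EC50.

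**What to change.** In SAP 7.2.1:

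1. Add site as a fixed term (two levels under the current protocol) to the dichotomous logistic model with BIS, age group and their interaction. Add it to the polytomous model where it can be estimated.
2. Report the site-adjusted 18-64 vs 65+ BIS50 contrast at a common site mix, beside the planned per-group curves. With a_g and b_g the intercept and slope for age group g, c the site coefficient and w a fixed center share used for both groups, BIS50_g = -(a_g + c w)/b_g.
3. Report it whether or not SAP 7.3 finds significant heterogeneity.
4. State that the term corrects a difference in mean threshold only, and that BIS95 and the interaction test remain open to center differences in slope or spread.

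Reconcile the SAP with protocol 5.1 on subjects, centers and the 50% cap in the same revision.

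The cost is SAP wording and one model term, with the standard error of the contrast changing by a few percent. No new data are needed. An exploratory display of BIS50 by age in years is optional; its absence is not an error in the plan.

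### SAP 7.2.1 does not account for four BIS-MOAA/S pairs per subject, so BIS50 and EC50 intervals and some age tests can be too optimistic

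*SAP*

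**What the plan says.** For the primary objective, SAP 7.2.1 states that "a polytomous logistic regression model will be employed to assess the relationship between the MOAA/S scale and the BIS score/age groups" and adds: "The interaction between age and BIS score will be included". It then says "Another dichotomous logistic regression model will be utilized as well", with MOAA/S split into responsive (2 to 5) and non-responsive (0 and 1). A two-parameter logistic curve follows, in which X is BIS or log concentration "and a & b are model parameters". From it come BIS50, BIS95 and "the effect-site concentration at which 50% subjects are unresponsive" for each age group, and "The corresponding 95% confidence intervals and standard errors for the estimates will be derived". Finally, "Multivariate logistic regression model will be used to study the effects of other baseline covariates". The general significance threshold is P<0.05.

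The data behind these models are repeated within subject. Protocol 10.6.3 scores MOAA/S before induction and after each of three propofol target steps; for the middle one, "This second step will also require depth of anesthesia assessment using MOAA/S". Protocol 10.6.5 records a BIS value ahead of each score. A fifth pair may exist: the synopsis places a check for MOAA/S 0 at the start of maintenance, while Protocol 10.6.4 places it at the start of induction. Those two places must be reconciled.

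Neither document mentions a random effect, GEE, repeated measures, clustered or robust variance, a bootstrap by subject, or one record per subject. The SAP's phrase about systematic variance between groups concerns age groups, not subjects.

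**The concern.** Four scores from one person are not four independent observations if people differ in the BIS value at which they stop responding. Someone who becomes unresponsive at an unusually high BIS tends to do so at every step. An ordinary logistic fit to stacked rows treats 100 subjects as 400 independent pairs and understates the error of anything estimated between subjects: BIS50, EC50, their age differences, and the effects of sex, blood panel, frailty or cognition. The SAP defines BIS50 and EC50 by the percentage of subjects who are unresponsive, yet the written formula has no subject level.

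BIS50 and EC50 by age group are the SAP's most direct estimates of whether the BIS-responsiveness relation shifts with age. If their intervals are too narrow, chance differences between the age groups will look more certain than they are. The SAP's introduction says these analyses may go into regulatory submissions and manuscripts.

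**Working it through.** The plan gives no precision figure for BIS50 or EC50, so there is none to reproduce. The power statement in SAP section 6 concerns a shift between age groups and does not bear on this point. The check is a simulation with no true age or covariate effect.

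**Inputs from the documents.** Four pairs per subject (Protocol 10.6.3, 10.6.5); 100 subjects split 35/65 (Protocol section 6 and 14.1); total BIS SD 10 (SAP section 6); unresponsive = MOAA/S 0-1 and P<0.05 (SAP 7.2.1).

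**Assumptions.**
- Mean BIS 96/82/68/54 at the four assessments, capped at 100.
- BIS subject SD 6 and residual SD 8, so √(36+64) = 10.
- Logistic slope 0.15 per BIS point; cumulative-logit thresholds 58/65/72/80/88.
- Between-subject SD of the threshold 0, 5, 10 or 15 BIS points. The documents give no value.

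The latent intraclass correlation is (0.15·SD)² / [(0.15·SD)² + π²/3]. For SD 10 this is 2.25/(2.25+3.29) = 0.41; for SD 0, 5 and 15 it is 0, 0.15 and 0.61. SD 15 is a high case.

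**Formulas.** With logit P = a + bX, BIS50 = −a/b. Its delta-method variance is g′Vg, with g = (−1/b, a/b²). The default V is the inverse information I⁻¹. The subject-clustered V is I⁻¹(Σ sᵢsᵢ′)I⁻¹, where sᵢ is subject i's summed score. The polytomous model was taken as a cumulative logit with BIS, age group and their interaction. BIS50 coverage is judged against the pooled-fit value from a very large sample. With 4,000 replicates, simulation error is about ±0.7 point at 5%.

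**Results with default errors, by threshold SD (nominal 95% and 5%).**

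| Quantity | 0 | 5 | 10 | 15 |
|---|---|---|---|---|
| BIS50 coverage, either age group | 95% | 93% | 90% | 87% |
| BIS50 age-difference test | 4.9% | 6.7% | 9.7% | 12.8% |
| Dichotomous model, age, no interaction | 4.9% | 6.6% | 10.5% | 14.3% |
| Subject-level covariate | 5.7% | 6.4% | 10.9% | 15.2% |
| Polytomous: joint age test | 5.0% | 7.4% | 11.8% | 16.6% |
| Polytomous: age contrast at BIS 70 | 5.3% | 8.4% | 14.8% | 20.3% |
| Polytomous: age-by-BIS interaction | 5.4% | 4.0% | 3.6% | 3.5% |
| Polytomous: age coefficient at BIS 0 | 5.0% | 4.5% | 4.2% | 4.1% |

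The mean default standard error of the BIS50 age difference is 100, 92, 84 and 78% of its true SD. At SD 10 the reported interval is about ±5.2 BIS points where about ±6.3 is needed.

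**EC50.** The pre-induction pair has no log concentration, so three steps remain. With an assumed slope of 6 per log unit and between-subject SD of log EC50 of 0, 0.125, 0.25 and 0.375, coverage was 95, 93-94, 89-90 and 88-89%.

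**BIS95.** Coverage was 92-94% at every SD, including 0, so clustering is not the cause.

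**With subject-clustered variance.** BIS50 coverage returns to 94-95% and the inflated tests to 4.6-6.5%.

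**Sensitivity.**
- Pre-induction score forced to awake, SD 5/10/15: BIS50 coverage 92-93/90/88%; joint age test 5.3/8.3/10.8%; contrast at BIS 70 8.5/12.5/16.1%.
- Fifth score forced to 0: BIS50 coverage 93-94/90/88-89%; joint test 5.8/7.3/8.8%.
- 200 subjects, as in the SAP, at SD 10: BIS50 coverage 90%, joint test 12.4%. More subjects do not cure it.
- Mean BIS 95/80/65/50 and different correlation assumptions: BIS50 coverage (18-64 group) 94/93/89/86% at SD 0/5/10/15.

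**The case against.** The strongest reply is that this is an omission, not a stated error. The SAP never says that pairs are pooled or independent, and defining BIS50 by percentage of subjects could fit a subject-level analysis. That is fair as far as it goes. But the SAP promises standard errors and intervals while leaving the unit of analysis and the variance method open, and a default logistic fit to the collected records gives the errors shown above.

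Second, some of the inflated tests are readings of the SAP. The one age term it singles out in the primary model is the interaction, which is not inflated. It does not define a joint age test, a contrast at BIS 70, or a dichotomous model without interaction. This stands, and it is why the BIS50 and EC50 intervals, which the SAP does specify, should carry the point.

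Third, the base case is unrealistic at its ends. At threshold SD 10 only 64% score MOAA/S 5 before any propofol and 5% score 0-1; at SD 15 the figures are 61% and 8%. Forcing realistic end scores brings the joint age test down to between 8.8 and 10.8% at SD 15. BIS50 coverage barely moves. The sizes for the polytomous tests are therefore soft; the BIS50 result is not.

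Fourth, the between-subject SD is unknown, and this is a feasibility study with no powered hypothesis (Protocol 14.1). Both are true. The size can only be given as a range, and the harm is limited.

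Finally, the SAP was written for protocol version 4, while the four-pair count comes from version 5.1. This does not help the SAP: the version history shows that MOAA/S was scored every 20 minutes before version 5.0, which means more repeats per subject.

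**Conclusion.** The concern holds. SAP 7.2.1 has no subject term, clustered variance or record-selection rule for data with at least four pairs per subject. If the pairs are pooled and subjects differ in threshold, 95% intervals for BIS50 and EC50 cover about 93% at a between-subject SD of 5 BIS points (or its assumed log-EC50 counterpart), about 90% at 10, and 87-89% at 15. A BIS50 age comparison then rejects a true null in about 7, 10 and 13% of studies. Tests of subject-level covariates and of age at mid-range BIS values over-reject as well. The age-by-BIS interaction and the age coefficient at BIS 0 do not, and BIS95 coverage is little affected. With no between-subject threshold variation there is no problem for BIS50, and at SD 5 the effect is small.

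The direction is secure; the size rests on an assumed SD and an assumed BIS profile. Because the study is unpowered and ties no decision to P<0.05, this should be fixed but does not threaten the study.

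**What to change.** Revise SAP 7.2.1 in three places.

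1. State which pairs enter each model. The pre-induction pair cannot enter the EC50 fit. Whether there is a fifth pair depends on reconciling the synopsis with Protocol 10.6.4.
2. Fit the polytomous, dichotomous and covariate models with subject as the cluster: GEE with independence working correlation, or ordinary logistic regression with a subject-clustered sandwich variance. Either keeps the curve as a statement about the percentage of subjects.
3. Derive intervals for BIS50, BIS95, EC50 and their age-group differences from the cluster-robust errors, or from a bootstrap that resamples whole subjects within age group. BIS95 is included for consistency.

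The cost is SAP wording and a procedure option, with no new data. Intervals will usually be wider, and there is slightly more analysis work. The SAP needs revision anyway: it still follows protocol version 4 with 200 subjects, against 100 in version 5.1.
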